13. STATISTICAL CONSIDERATIONS

13.1. Analysis Sets

The following three analysis sets are defined:

Confidential Page 62 of 86

- Intent-to-Treat (ITT) analysis set consists of all subjects for whom TBS was identified. Subjects who do not complete the procedure after TBS identification will be included in the ITT.
- Per-Protocol (PP) analysis set (set of evaluable subjects) consists of all ITT subjects who have no major protocol deviations and have data available for primary effectiveness endpoint.
- Safety analysis set consists of all subjects who received study product.

The primary effectiveness endpoint will be analyzed using the ITT and the PP sets. However, the primary analysis will be based on the PP set. The ITT analysis will be considered supportive.

All secondary effectiveness endpoints will be analyzed using the ITT set, while safety endpoints will be analyzed using the Safety set.

It is not anticipated that there will be data missing for the primary or secondary effectiveness endpoints, but, if there is, the analyses based on the ITT set will consider missing data as failures for these endpoints. Missing data for safety endpoints will not be imputed.

Major protocol deviations are deviations that have an impact on the primary effectiveness endpoint. These will be determined prior to database lock.

13.2. Statistical Design, Method and Analysis Procedure

This is a single blind, randomized, prospective study comparing SURGICEL Powder with SURGICEL Original (control) as an adjunct to achieve hemostasis in the control of capillary, venous, and small arterial hemorrhage when ligation or other conventional methods of control are impractical or ineffective during surgery (open, laparoscopic, or thoracoscopic) in Chinese adult patients.

Subjects will be randomly assigned to either SURGICEL Powder (Test) or SURGICEL Original (Control) in a 1:1 allocation ratio. Randomization will be stratified by investigational site and TBS bleeding severity (mild or moderate bleeding).

Two analyses will be performed. The first analysis will occur after all subjects complete phone call or office visit [30 days (+ 14 days) post-surgery]. All data collected through 30-day (+14 days) follow-up will be analyzed. The second analysis will occur after all subjects complete phone call or office visit [6-month (+/-30 days) post-surgery] and the data collected at this follow-up is available. The second analysis will be performed on the data from the 6-month follow-up assessing any occurrences of SAEs requiring surgical intervention and assessed as possibly related or related to the randomized study treatment.

Confidential Page 63 of 86

The **primary effectiveness endpoint** is defined as the proportion of subjects achieving hemostatic success at 5 minutes following the application of SURGICEL Powder or SURGICEL Original with no re-bleeding requiring additional treatment at the TBS any time prior to initiation of final fascial closure.

This is a non-inferiority trial with a 10% margin and the statistical analysis comparing treatment groups for primary effectiveness endpoint performed at one-sided significance level of 0.025 and 80% power. The true success rates are assumed to be 85% in the SURGICEL Powder (Test) group and 80% in the SURGICEL Original (Control) group. 14, 15, 16, 17. For the justification of the assumed success rates in the two treatment groups, see Section 7.

Study Hypothesis

The statistical hypothesis for testing the treatment group difference for primary effectiveness endpoint is presented as follows:

• H_0 : P_T – $P_C \le -0.1$ tested against the alternative hypothesis

 H_1 : $P_T - P_C > -0.1P_C$ proportion of successes in Control group, and P_T is the proportion of successes in Test group.

For the primary effectiveness endpoint, a one-sided 97.5% confidence interval for P_T - P_C will be constructed using the Farrington-Manning (FM) score method. If the lower limit of the one-sided 97.5% confidence interval is greater than -0.1, then it will be concluded that the SURGICEL Powder is non-inferior to SURGICEL Original. If the non-inferiority of SURGICEL Powder is established, the superiority of SUGICEL Powder to SURGICEL Original will then be evaluated; if the lower limit of one-sided 97.5% confidence interval is greater than 0, then it will be concluded that the SURGICEL Powder is superior to SURGICEL Original. In addition, two-sided 95% confidence intervals for the proportion of successes in each treatment group separately will be constructed using the Clopper-Pearson method.

The primary endpoint will be analyzed using the Intent-to-Treat (ITT) and Per-Protocol (PP) sets. The PP analysis will be considered the primary analysis, while the ITT analysis will be considered supportive. The analysis sets for this study are defined in Section 13.1.

The following **secondary efficacy endpoints** will be summarized descriptively by treatment group and overall, for the ITT analysis set:

Confidential Page 64 of 86

- Proportion of subjects achieving hemostatic success at 3 minutes following the application of SURGICEL Powder or SURGICEL Original with no re-bleeding requiring additional treatment at the TBS any time prior to initiation of final fascial closure;
- Proportion of subjects achieving hemostatic success at 10 minutes following the
 application of SURGICEL Powder or SURGICEL Original with no re-bleeding
 requiring additional treatment at the TBS any time prior to initiation of final
 fascial closure.

For the binary (success/failure) secondary effectiveness endpoints (3 and 10 minutes hemostasis endpoints), within-treatment group two-sided 95% confidence intervals will be reported for the proportion of successes using the Clopper-Pearson method. A two-sided 95% confidence interval for the difference in proportion of successes between treatment groups (Test minus Control) will also be calculated for each binary secondary effectiveness endpoint using the FM score method; however, no testing for non-inferiority will be carried out.

In addition, the following **safety endpoints** will be summarized descriptively by treatment group and overall, for the Safety analysis set:

- Incidence of thromboembolic events that were assessed as possibly related or related to the study treatment (from enrollment through the 30-day follow-up phone call or office visit);
- Incidence of post-operative re-bleeding that was assessed as possibly related or related to the TBS and requiring medical/surgical intervention (from initiation of final fascial closure through the 30-day follow-up phone call or office visit);
- Incidence of SAEs requiring surgical intervention and assessed as possibly related or related to the study treatment (from enrollment through the 6-month follow-up phone call or office visit)

The incidence of adverse events (AEs) will be assessed at the preferred term level using the Medical Dictionary for Regulatory Activities (MedDRA) for event categorization. Incidence of AEs will also be assessed by onset time (intraoperative or postoperative), relationship to study surgical procedure, relationship to the study product, severity, and seriousness.

All continuous variables will be summarized by number of subjects, mean, standard deviation, median, minimum and maximum. All categorical data will be summarized by frequencies and associated percentages. No inferential statistics will be generated for

Confidential Page 65 of 86

secondary efficacy and safety endpoints.

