10.1.13. Safety Evaluation Method

Description of safety parameters

The safety parameters in this study are the following:

- Incidence of thromboembolic events that were assessed as possibly related or related to the study treatment (from enrollment through the 30-day follow-up phone call or office visit);
- Incidence of post-operative re-bleeding that was assessed as possibly related or related to the TBS and requiring medical/surgical intervention (from initiation of final fascial closure through the 30-day follow-up phone call or office visit);
- Incidence of serious adverse events requiring surgical intervention and assessed as possibly related or related to the study treatment (from enrollment through the 6-month follow-up phone call or office visit)

Selection of method and time to evaluate, record, and analyze the safety parameters

Subjects will be assessed for all AEs and SAEs from time of ICF through the 30-day follow-up. At the 6-month follow-up, only SAEs requiring surgical intervention and assessed as possibly related or related to the study treatment, will be reported. The safety

Confidential Page 49 of 86

parameters are recorded on the e-CRF according to the Investigator's record, medical record, and all other related source documents, which are collected at each follow-up visit.

Sponsor's Medical Director (Study Medical Monitor/Safety Lead) will assess all serious adverse events for causality and expectedness and will utilize Ethicon's Product Safety Committee (PSC) to review and adjudicate the following safety signals:

- Thromboembolic events
- Postoperative re-bleeding
- Reoperations for complications assessed as possibly related or related to the study treatment

The PSC will also review cumulative safety data from the study. The PSC will advise on the continuing safety of study subjects and those yet to be recruited to the study. Based on cumulative data from the study, the PSC may recommend whether to continue, suspend, modify, or stop the study. At the conclusion of the study, the PSC will also give a final assessment of the safety of the product from this study. The composition, responsibilities, frequency of PSC meetings, handling of emergency situations, and documentation of PSC meetings will be specified in the Safety Management Plan (SMP).

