11.4.3. Activities and Information Collected During Surgical Procedure

The following activities will be performed and the following information will be collected during the surgical procedure:

- Review of inclusion and exclusion criteria to confirm intra-operative eligibility.
 If a subject is no longer eligible, the reason for the screen failure will be documented in the source documentation and the screening log.
- Concomitant medications, as outlined in Section 11.3.5
- Hospital admission date (for overall Length of Stay)
- Entry and exit time.
- Primary surgical procedure information: open, laparoscopic, thoracoscopic. surgical specialty (general, cardiothoracic, gynecological and the type of procedure).
- Procedure time (first incision to final wound closure).
- Randomization, as outlined in Section 11.3.6.
- Assessment and determination of hemostasis at TBS
- Estimated Blood Loss (EBL)
- Transfusion information (if applicable). Amount and blood product(s) used and the type of product (e.g., red blood cells, fresh frozen plasma, platelet concentrate, etc.).
- Hemostatic methods used at the TBS prior to randomization (none, [other

Confidential Page 57 of 86

methods are impractical], suture, ligation, cautery, other.

- TBS information: Parenchyma or soft tissue type and location
- Size of TBS (length, width)
- Heparin use and time of reversal (if applicable)
- Total number of units used (SURGICEL Powder or SURGICEL Original)
- Adverse events, including any complications possibly related or related to bleeding and/or thromboembolic events.
- Drain information (if applicable)
- Surgeon Ease of Use Questionnaire—one questionnaire needs to be completed per Investigator for their first 2 cases using SURGICEL Powder (completed as soon as possible, but within approximately 72 hours).

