11.5. Post-Surgery until Hospital Discharge

Prior to discharge, the following data will be recorded:

- Changes in concomitant medications.
- Was drain used, if yes record days, quantity and describe content (type of the discharge, e.g. serosal fluid, blood, etc.).
- Physical examination (vital signs: BT, BP, HR and RR) for 3 consecutive days or until hospital discharge, whichever comes first.
- CBC with Hgb test prior to discharge.
- Adverse events, including reoperation, any complications possibly related to bleeding and/or thromboembolic events.
- Date of hospital discharge (for overall Length of Stay).

11.6. 30-day Follow-Up Phone call or Office Visit (+ 14 days)

The following information will be recorded at the clinical follow-up phone call or office visit approximately 30 days following the study surgery:

- Changes in concomitant medications, including use of any blood products following hospital discharge.
- Adverse events, including any reoperations and/or complications possibly related or related to bleeding and/or thromboembolic events.

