6.2. BASELINE

Unless otherwise specified, baseline is defined as the last non-missing measurement taken prior to reference start date (including unscheduled assessments). In the case where the last non-missing measurement and the reference start date coincide, that measurement will be considered prebaseline, but Adverse Events (AEs) and medications commencing on the reference start date will be considered post-baseline.

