14.1.1. ANALYSIS OF SAFETY ENDPOINTS

All AEs reported during the study will be coded to the Medical Dictionary for Regulatory Activities (MedDRA). All AEs will be summarized descriptively by MedDRA system organ class and preferred

term in each treatment group and in total.

Incidence of AEs will also be summarized descriptively by relationship to study surgical procedure, relationship to the study product, severity, and seriousness.

The specific safety endpoints and other adverse events will be summarized descriptively in each treatment group and overall by presenting the number and percentage of subjects experiencing the occurrence of each event.

In addition, within each TBS bleeding severity level (Mild, Moderate) and overall, the specific safety endpoints listed in section 14.1 will be summarized descriptively by treatment group and overall, using frequency counts and associated percentages.

All outputs for safety outcomes will be based on the Safety analysis set.

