14.7. CHANGES FROM THE PROTOCOL SPECIFIED ANALYSIS

-For clarity, "relationship to TBS" was changed to "relationship to study treatment" in the definition of the following safety endpoint: "Incidence of post-operative re-bleeding that was assessed as possibly related, probably related, or related to the study treatment and requiring medical/surgical intervention (from initiation of final fascial closure through the 30-day follow-up phone call or office visit)".

-The text defining the PP set and major protocol deviations was changed from:

"Per-Protocol (PP) analysis set (set of evaluable subjects) consists of all ITT subjects who have no major protocol deviations and have data available for primary effectiveness endpoint. Subjects will be classified according to randomized treatment. Major protocol deviations are deviations that have an impact on the primary effectiveness endpoint. These will be determined prior to database lock."

to:

"Per-Protocol (PP) analysis set (set of evaluable subjects) consists of all ITT subjects who have no major protocol deviations affecting the primary effectiveness endpoint and have data available for this endpoint. Subjects will be classified according to randomized treatment. Major protocol deviations will be determined prior to database lock."

This change is required to maintain consistency with the manner in which the assessment of the major protocol deviations was performed for this study - major deviations that do not affect the primary effectiveness endpoint did not exclude subjects from the PP set.

The text defining the SS set was changed from:

"Safety analysis set consists of all subjects who received study product. Subjects will be classified according to treatment received."

to:

"Safety analysis set consists of all subjects who received study product. Subjects will be classified according to actual treatment received and at least post-baseline follow up"

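### The SAP drops the protocol's intra-operative/post-operative AE breakdown without declaring it and, separately, has no rule to set apart AEs that began before the product was applied

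*Protocol*

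**What the plan says.** **Planned breakdowns.** Protocol 13.2 names five ways to break down AE incidence, with phase of onset first: "Incidence of AEs will also be assessed by onset time (intraoperative or postoperative", followed by link to the procedure, link to the product, severity and seriousness. The matching sentence in SAP 14.1.1 is: "Incidence of AEs will also be summarized descriptively by relationship to study surgical procedure, relationship to the study product, severity, and seriousness". The table list in SAP 14.2 covers all serious AEs, all AEs, AEs by maximum severity, AEs by strongest relationship and AEs leading to discontinuation. None is by onset.

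**Declared changes.** SAP 14.7, headed "CHANGES FROM THE PROTOCOL SPECIFIED ANALYSIS", lists three: the wording of the re-bleeding endpoint, the per-protocol set and the safety set. Protocol 13.9 requires changes from the planned analyses to be specified in a protocol revision or in the SAP.

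**Timing rules.** SAP 6.1 sets the reference start as the day of surgery, and SAP 6.2 adds that "Adverse Events (AEs) and medications commencing on the reference start date will be considered post-baseline". Randomization and application take place during the operation, once a target bleeding site has been found (Protocol 11.3.6).

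**Start of AE collection.** Protocol 10.1.13 says "Subjects will be assessed for all AEs and SAEs from time of ICF through the 30-day follow-up". Protocol 19.2.2 and 19.6 start at enrollment. Table 1 marks AEs in the surgical-procedure column and later, with no mark under screening or baseline.

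**The concern.** There are two separate gaps.

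The first is traceability. A planned safety breakdown is absent from the SAP with no statement that it was dropped or why. It is also a useful one: the investigator who rates relatedness cannot be blinded (Protocol 11.3.6, 19.5), and phase of onset depends less on judgment than a relatedness rating does.

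The second is what the arm-by-arm AE tables count. An event that began during anesthesia or dissection, before the product was applied, cannot be an effect of the product. If such events are included, both arms carry the same background in expectation and any real difference looks smaller. A further SAP 14.2 rule counts an AE with missing causality as probably related, so a pre-application event with that field blank would appear as product-related. Protocol section 7 says there has been no clinical investigation of SURGICEL Powder, so these descriptive tables carry much of the safety description.

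**Working it through.** **Step 1: compare the lists.**

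| Breakdown of AE incidence | Protocol 13.2 | SAP 14.1.1 / 14.2 | Declared in SAP 14.7 |
|---|---|---|---|
| Onset, intra- or post-operative | yes | no | no |
| Link to procedure | yes | yes | not needed |
| Link to product | yes | yes | not needed |
| Severity | yes | yes | not needed |
| Seriousness | yes | yes | not needed |

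**Step 2: what each rule would separate.** Divide the time line into (a) consent to the start of surgery, (b) start of surgery to application, (c) application to closure and (d) after closure.

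- The protocol's split puts b and c together as intra-operative and d as post-operative. It does not separate b from c.
- SAP 6.2 labels b, c and d post-baseline alike.
- The SAP 14.2 tables of all AEs state no onset restriction, so they count whatever is collected from a to d in subjects in the safety set.
- A treatment-emergent rule would count c and d only.

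The missing split and the missing treatment-emergent rule are therefore independent. Restoring the first does not supply the second.

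**Step 3: which pre-application events are collected.**

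- From consent (Protocol 10.1.13): a and b. Screening may be up to 21 days before surgery.
- From the surgical-procedure column (Table 1, Protocol 11.4.3): b.
- From enrollment (Protocol 19.2.2, 19.6): almost none. Protocol 11.1 makes an identified bleeding site part of enrollment. Protocol 10.1.8 requires all inclusion criteria to be met, and criterion 4 is a bleeding site found during surgery. Randomization and application then follow immediately (11.3.6).

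**Step 4: form of the dilution.** The plan states no AE rate, so there is no figure of its own to reproduce. Let a_T and a_C be the proportions with an AE after application, and b the proportion with one before it, equal in the arms and independent of later AEs. Then

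observed difference = [1 − (1 − a_T)(1 − b)] − [1 − (1 − a_C)(1 − b)] = (1 − b)(a_T − a_C).

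With assumed values a_T = 30% and a_C = 20%:

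| b (assumed) | Test | Control | Difference, points | Ratio |
|---|---|---|---|---|
| 0% | 30.0% | 20.0% | 10.0 | 1.50 |
| 5% | 33.5% | 24.0% | 9.5 | 1.40 |
| 10% | 37.0% | 28.0% | 9.0 | 1.32 |
| 20% | 44.0% | 36.0% | 8.0 | 1.22 |
| 30% | 51.0% | 44.0% | 7.0 | 1.16 |

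Every input in this table is an assumption. It shows the direction and form of the effect, not its size in this trial.

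**The case against.** The strongest reply is that the omission is a small mismatch with little consequence. Enrollment is the start point in most of the AE sections, and it needs an identified bleeding site, so the pre-application window is short. Table 1 has no AE mark before surgery, and Protocol 11.1.1 records no AEs for screen failures. The three safety endpoints are filtered by relatedness or, for re-bleeding, start at closure. Safety analyses are descriptive, and pre-randomization events are balanced in expectation. All of this stands and limits the size. It does not explain the undeclared omission, and it leaves Protocol 10.1.13 in conflict with the enrollment-based sections.

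Three stronger readings are tempting, and the documents do not support them.

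- *A reader might infer that dropping the split is what lets pre-application events into the tables.* Step 2 shows otherwise: the split would leave those events in the intra-operative category and the all-AE tables unchanged.
- *A reader might infer from Protocol 19.6, which lists an onset date and no time, that phase cannot be recovered.* That section lists items for the source documents. The eCRF and the output template (SAP section 8) are not available. AEs are collected as a separate activity during surgery ("Adverse events, including any complications possibly related or related to bleeding and/or thromboembolic events") and again before discharge ("Adverse events, including reoperation, any complications possibly related to bleeding and/or thromboembolic events"), and procedure time and the clock time of T0 are recorded. Phase may already be captured, although no document says it will be used.
- *A reader might infer that post-operative re-bleeding cannot be placed in time.* Table 1 collects it only in the post-surgery and 30-day columns, and bleeding before closure is covered by the T_F assessment and the failure rules in Protocol 11.4.9.

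**Conclusion.** The point holds in two parts. First, an AE breakdown planned in Protocol 13.2 is missing from the SAP and is not declared in 14.7, contrary to Protocol 13.9. This rests on the text alone, with the caveat that the SAP's output template was not seen. Second, the SAP has no treatment-emergent rule, although the product is applied during surgery. Pre-application AEs then enter the arm-by-arm tables if collection starts at consent or at the start of surgery. The effect is a modest dilution of a descriptive contrast, by the factor (1 − b) under equal and independent background rates. The value of b is unknown, and near zero if collection starts at enrollment. The expected direction favors neither arm, and the primary analysis is untouched. This is worth correcting because it is specific and cheap, not because it threatens the trial's conclusion.

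**What to change.** 1. Restore the intra-operative/post-operative AE table in SAP 14.1.1 and 14.2. If it is deliberately dropped, say so in 14.7 with the reason.
2. Define treatment-emergent AEs in the SAP as those with onset at or after product application, count these by arm, and list earlier AEs separately. The wall-clock time of T0 is already recorded (Protocol 11.4.4). Because T0 marks the completion of application, state that an event arising while the product is being applied counts as treatment-emergent.
3. Check that the AE record holds onset phase, or a clock time for Day 1 events. Add it if it does not.
4. Reconcile the start of AE collection in Protocol 10.1.13 with 19.2.2, 19.6 and Table 1.

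The cost is one extra table, one definition and possibly one AE field. SAP 14.7 describes the deviation review in the past tense, so conduct may be well advanced and the phase of past events may have to be retrieved from source records. Overall AE percentages would be slightly lower.
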